2.2.2.3 PRIMARY SAFETY ENDPOINT

The primary safety endpoint is the rate of occurrence of Grade 1 or greater rectal adverse events and implantation procedure related adverse events with a duration of at least 2 days through 6 months. This rate will be compared between the balloon group and the control group, and the study will be considered a success if statistical significance is achieved on a one-sided non-inferiority test. Details appear in **Section 2.3**.

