2.3.3 ADJUSTMENTS FOR MULTIPLICITY

The hypothesis tests for two primary endpoints will be considered independently without adjustment for multiplicity since both tests must reach significance for the study to successfully support the clearance of the balloon device. If both endpoints reach success for the study as outlined below, then three analyses will be performed for consideration in labeling by testing for the superiority of the balloon to the *Control Group*.

- The primary safety endpoint will be evaluated using a two-sided Fisher's Exact test in order to assess superiority of the balloon safety.
- The secondary endpoint rate of Grade 2 or greater rectal adverse events or implantation procedure related adverse events with a duration of at least 5 days will be evaluated using a two-sided Fisher's Exact test.
- The secondary endpoint of the degree of all GU acute toxicity as determined by the Expanded Prostate Cancer Index Composite (EPIC) at the last day of IMRT will be evaluated using a two-sided Rank-Sum (Wilcoxon) test.

The additional endpoints will be evaluated using two-sided tests. If any of these should reach significance at the 0.0167 level, then the results would be considered to be supportive of an additional claim or claims (e.g. a Bonferroni will be used to control for multiplicity).

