2.3.4.1 PRIMARY SAFETY ANALYSES

The primary safety endpoint is based on the occurrence of Grade 1 or greater rectal adverse events and implantation procedure related adverse events with a duration of at least 2 days through the first six months. Subjects will be counted as having an event if one occurs anytime through Day 197 from the marking date (6 months plus up to 14 days) or as not having an event if they record no events and are followed for at least Day 169 (6 month minus 14 days) from the marking date. A one-sided test of non-inferiority will be completed using the Farrington-Manning method with a non-inferiority bound of 15%. If we denote the s_{pr} to the safety event rate in the *balloon Group* and s_c to be the safety event rate in the *Control Group*, the hypothesis is as follows:

$$H_0: \, s_{pr} - s_c \geq 0.15 \ vs \ H_1: \ s_{pr} - s_c < 0.15$$

The study will be a success if the test is significant against a one-sided p-value cut-off of 0.025.

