2.3.4.5 SECONDARY ENDPOINTS

Secondary Safety endpoints include:

- The rate of Grade 2 or greater rectal or implantation procedure related adverse events with a duration of at least 5 days and implantation procedure related adverse events in the *Balloon Group* subjects compared to *Control Group* subjects in the 6 month follow-up period post marking and/or balloon implantation.
- Degree of all GU acute toxicity as determined by the Expanded Prostate Cancer Index Composite (EPIC).

The adverse event endpoint will be analyzed using a Fisher's Exact test. The EPIC endpoint will be modeled by visit using a repeated measures model with an unstructured covariance matrix.

Secondary efficacy endpoints include:

- Additional dosimetry parameters (D_{Rectum}100, D_{Rectum}90, D_{Rectum}80, D_{Rectum}70) will be evaluated in the balloon arm only, where subjects will serve as their own control (dosimetry reduction after balloon implantation) as the dosimetry parameters are compared to their baseline values per subject.
- Core lab evaluation of distance of rectal wall from the prostate at baseline and last XRT visit. This data will be measured and quantified.

These are all numeric measures and will be compared between groups using Rank-Sum tests.

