2.3.6 RISK ANALYSIS

Following is a list of potential adverse events for this study. These include events that have been identified by nature, severity, or frequency in the current literature or in the investigational plan.

2.3.6.1 **RISKS**

Risks associated with the use of the BioProtect Balloon Implant System in conjunction with the control procedure (marking and IMRT) are expected to be comparable to the risks associated with the control procedure alone. *Risks associated with radiation therapy include:*

- Acute urinary retention (usually related to general anesthesia administration);
- Bladder neck constriction or stricture;
- Fatigue;
- Fragility fractures (if hormone use is added to the treatment);
- Hemospermia (blood in the sperm);
- Hot flashes (if hormone use is added to the treatment);

- Erectile dysfunction;
- Pruritis;
- Radiation cystitis or urethritis;
 - o Bladder spasms,
 - Burning with urination,
 - Dysuria (difficulty emptying bladder),
 - Hematuria (blood in the urine),
 - Nocturia (need to urinate during sleeping hours),
 - Urgent, frequent urination.
- Radiation enteritis;
 - o Gas,
 - Bowel urgency,
 - Abdominal pain,
 - Abdominal tenderness.
- Rectal-anal mucositis (irritation and ulceration);
- Radiation proctitis and other rectal side-effects;
 - Burning with bowel movements,
 - o Diarrhea,
 - Hematochezia (blood in the stool),

- Loose stools.
- Rectal bleeding,
- Rectal fistula,
- Rectal ulcer,
- Straining.

- o Hemorrhoids,
- Tenesmus (feeling of incomplete defecation);
- Urinary incontinence;
- UTI;
- Vasovagal episode (usually caused by severe straining).

Risks associated with marking and/or spacer implantation procedure include:

- Fever greater than 100°;
- Site bleeding mild to moderate;
- Site hematoma temporary, self terminated;
- Site infection and related symptoms Infection along the trajectory of the insertion of surgical tools, including the site of implantation;
- Rectal wall puncture.

Risks specifically associated with the BioProtect Balloon Implant Systeminclude:

- Erosion through a hollow organ wall such as bowels, urinary bladder, etc.;
- Incomplete absorption;
- Inflammatory reaction;
- Migration of the device from the desired location;

- Needle penetration into bloodstream, bladder, prostate, rectal wall, rectum or urethra;
- Premature balloon deflation;
- Prolonged or delayed procedure;
- Rectal perforation;
- Tissue necrosis.

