This study has co-primary endpoints for safety and efficacy. The primary safety endpoint is the rate of Grade 1 or greater rectal adverse events lasting at least 2 days through the first 183 days (six months) that are device-related or marking/implantation procedure-related. The primary efficacy endpoint will be evaluated with a one-sided test of non-inferiority using the Farrington-Manning method with a non-inferiority bound of 15%. If  $s_{pr}$  denotes the safety event rate in the *ProSpace Group* and  $s_c$  denotes the safety event rate in the *Control Group*, the primary safety hypothesis is as follows:

$$H_0: s_{pr} - s_c \ge 0.15$$
 vs  $H_1: s_{pr} - s_c < 0.15$ 

The primary efficacy endpoint is a binary assessment of whether a subject obtains at least a 25% reduction at 21 days post-implantation in the volume of the rectum receiving greater than or equal to 70 Gy ( $V_{Rectum}$  70). The primary efficacy endpoint will be assessed only for subjects who are randomized to the ProSpace Group and receive the ProSpace device, and it will be evaluated using a one-sided 0.025 exact binomial test. If we denote ve to be the percentage of subjects meeting the VRectum 70 success criteria in the *ProSpace Group*, the primary hypothesis is as follows:

$$H_0: v_e \le 75.0\%$$
 vs  $H_1: v_e > 75.0\%$ 

The hypothesis tests for the two co-primary endpoints will be considered independently without adjustment for multiplicity since both tests must reach significance for the study to successfully support the clearance of the ProSpace device. The study will be successful if both the primary safety endpoint and primary efficacy endpoint both reach statistical significance in the tests outlined above against one-sided p-value cut-offs of 0.025.

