#### 10.3.4.1 Co-Primary Safety Endpoint and Analysis

#### 10.3.4.1.1 Primary Safety Endpoint

The adverse events qualifying as primary safety events will be determined through adjudication by the CEC. The primary safety endpoint is based on the occurrence of one or more adverse event as follows, as indicated on the CEC CRF:

- Event is indicated to be a Grade 1 or greater rectal event lasting at least 2 days through the first 183 days (6 months) and
- Event meets one of the relatedness classifications:
  - Event is indicated to possible, probably, or definitely device-related;
  - Event is related to marking or
  - Event is related to the balloon implantation procedure.

Note that events related to anesthesia or to the use of a foley catheter will not be considered marking or implantation procedure-related.

Subjects will be counted as having an event if one occurs anytime through Day 183 (6 months) from the marking date or as not having an event if they record no events and are followed through at least Day 169 (6 month minus 14 days) from the marking date. Subjects who terminate the study before Day 169 and did not experience the AE of interest will be considered missing from the PP population and not included in the primary safety analysis. The impact of these subjects will be evaluated in a sensitivity analysis for the primary safety endpoint as described below.

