# 12 List of Tables, Figures and Listings

Tables
Table 14.1.1.1, Study Enrollment, All Subjects
Table 14.1.1.2, Study Enrollment by Site, Intent-to-Treat Population
Table 14.1.1.3, Subject Follow-Up, Per Protocol Population
Table 14.1.1.4, Protocol Deviations, Per-Protocol Population
Table 14.1.2.1, Demographics, Per-Protocol Population
Table 14.1.2.2, Demographics, Intent-to-Treat Population
Table 14.1.3.1, Medical History, Per-Protocol Population
Table 14.1.3.2, Medical History, Intent-to-Treat Population
Table 14.1.3.3.1, Medications at Screening, Per-Protocol Population
Table 14.1.3.3.2, Medications at During Study, Per-Protocol Population
Table 14.1.4.1, Study Procedure Information, Per-Protocol Population
Table 14.1.4.2, Study Procedure Information, Intent-to-Treat Population
Table 14.2.1.1, Primary Analysis of Reduction in V Rectum 70, ProSpace Per-Protocol Population
Table 14.2.1.2, Tipping Point Analysis of Reduction in V Rectum 70, ProSpace Intent-to-Treat Population
Table 14.2.1.3, Covariate Analyses for Reduction in V Rectum 70, ProSpace Per-Protocol Population
Table 14.2.1.4, Summary of Percentage Reduction in V Rectum 70, ProSpace Per-Protocol Population
Table 14.2.1.5, Dosimetry Parameters, ProSpace Per-Protocol Population
Table 14.2.1.6, Rectal Wall Distance, ProSpace Per-Protocol Population
Table 14.2.2.1, Primary Safety Analysis for Occurrence of Grade 1 or Greater Rectal Adverse Events, Per-Protocol
Population
Table 14.2.2.2, Primary Safety Analysis for Occurrence of Grade 1 or Greater Rectal Events Tipping Point
Analysis, Per-Protocol Population
Table 14.2.2.3, Primary Safety Endpoint Cumulative Safety Events by Time Kaplan-Meier Estimates, Per-Protocol
Population
Table 14.2.2.4, Covariate Analyses for Reduction in Primary Safety Endpoint Using Kaplan-Meier Method, Intent-
to-Treat Population
Table 14.2.2.5, Sensitivity Analysis for Occurrence of Grade 1 or Greater Rectal Events through Day 197, Per-
Protocol Population, Per-Protocol Population
Table 14.2.3, Analysis of Grade 2 or Greater Rectal or Procedure-Related Events of Duration of Two or More
Days, Per-Protocol Population
Table 14.2.6.1, Analysis of EPIC Urinary Incontinence Domain Scores by Timepoint, Per-Protocol Population
Table 14.2.6.2, Analysis of EPIC Urinary Incontinence Domain Scores at IMRT Midpoint and Final IMRT Visit,
Per-Protocol Population

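### Protocol and SAP define different co-primary safety endpoints: the SAP adds an attribution requirement that its list of changes does not name, and carries over rates and power that are unsupported for the endpoint it tests

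*SAP*

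**What the plan says.** Protocol 2.2.2.3 sets the endpoint, over a 6-month horizon, as a rate covering "Grade 1 or greater rectal adverse events and implantation procedure related adverse events with a duration of at least 2 days". Protocol 2.3.4.1 repeats it ("procedure related adverse events with a duration of at least 2 days through the first six months"). Rectal events need no attributed cause there.

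SAP 10.3.4.1.1 starts from a "Grade 1 or greater rectal event lasting at least 2 days through the first 183 days (6 months) and" then requires one of three CEC attributions: possibly, probably or definitely device-related; related to marking; or related to balloon implantation. SAP 5 says the same in one line ("lasting at least 2 days through the first 183 days (six months) that are device-related or marking/implantation procedure-related"), as does SAP 3.1. Anesthesia and foley-catheter events do not count as procedure-related.

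SAP 3.2 lists the move from Day 197 to Day 183, the Kaplan-Meier clarification, CEC adjudication, the anesthesia/foley rule, the EPIC domains and the Sign-Rank test. It does not say that a rectal event must now be attributed.

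SAP 6 repeats the planning case of Protocol 2.3.4.4.2: 21% Control, 19% balloon, a 15-point margin and 85% power. It adds only that CEC-adjudicated events will be used.

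**The concern.** This test decides study success jointly with efficacy, so both documents should define the same event. The attribution condition also works differently by arm. Every subject is marked, but only the balloon arm has a device and an implantation. The same rectal complaint during IMRT can count in one arm as possibly device-related and not count in the other. Rectal events attributed only to IMRT, where a spacer's benefit would appear, leave the comparison.

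Two things follow. The result of a randomized comparison comes to depend on committee judgement in one arm. And the sample-size argument describes an endpoint that may not be the one tested.

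**Working it through.** **1. The definitions side by side.** The protocol's *and* is loose.

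- Protocol 2.3.3 words the parallel Grade 2 endpoint with *or*: "Grade 2 or greater rectal adverse events or implantation procedure related adverse events with a duration of at least 5 days".
- Protocol 2.3.4.5 uses both words: "Grade 2 or greater rectal or implantation procedure related adverse events with a duration of at least 5 days and implantation procedure related adverse events".
- The list in Protocol 2.3.6.1 opening "Risks associated with marking and/or spacer implantation procedure include" has five items (fever, site bleeding, site hematoma, site infection, rectal wall puncture). Only the last is rectal.

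These favour a union of two event types.

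| Event lasting at least 2 days | Protocol, union | Protocol, intersection | SAP |
|---|---|---|---|
| Rectal, attributed only to IMRT | counts | no | no |
| Rectal, implantation-related | counts | counts | counts |
| Rectal, device-related only | counts | no | counts |
| Non-rectal, procedure-related | counts | no | no |

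The SAP column matches neither protocol column. Neither protocol reading has a device-relatedness route.

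**2. Reproducing the 85%.** Inputs (Protocol 2.3.4.4, SAP 6): 136 balloon and 68 Control evaluable, rates 19% and 21%, margin 0.15, one-sided 0.025. The Farrington-Manning statistic is

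Z = (p_b − p_c − 0.15) / √[r_b(1−r_b)/136 + r_c(1−r_c)/68],

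where r_b and r_c are the maximum-likelihood rates restricted to r_b − r_c = 0.15. The test passes if Z ≤ −1.96.

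- At 19% and 21% the restricted rates are 27.2% and 12.2%, giving a null standard error of 0.0550.
- The standard error at the assumed rates is √(0.19×0.81/136 + 0.21×0.79/68) = 0.0598.
- Power = Φ[(0.17 − 1.96×0.0550)/0.0598] = Φ(1.04) = 85.1%.
- Exact enumeration of all 137 × 69 outcomes gives 86.0%.

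The plan's arithmetic is right for those rates.

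**3. How the pass limit moves with the Control count** (same enumeration). At 21%, 68 × 0.21 ≈ 14 Control events are expected. The documents give no rate for rectal events qualifying through marking alone. I assume 1%, 3% or 5%, which gives 0.7, 2.0 or 3.4 expected events.

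| Control events of 68 | Most balloon events of 136 that pass |
|---|---|
| 0 | 12 (8.8%) |
| 1 | 13 (9.6%) |
| 2 | 14 (10.3%) |
| 3 | 16 (11.8%) |
| 14 | 32 (23.5%) |

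**4. Type I error.** With a true 15-point difference on the tested endpoint and Control rates from 0 to 21%, the exact pass probability is 2.1% to 2.8%.

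**5. Sensitivity to attribution (illustration only).** Let m be the Control marking-only rate (assumed 1/3/5%), T the balloon all-cause rate, and f the share of the balloon arm's other events attributed to device or implantation. The qualifying balloon rate is m + f(T − m). Non-rectal events are ignored.

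| True all-cause rates | f | Pass probability, m = 1/3/5% |
|---|---|---|
| 19% vs 21% | 25% | 97/94/90% |
| 19% vs 21% | 50% | 47/50/55% |
| 19% vs 21% | 75% | 6/12/20% |
| 36% vs 21% | 10% | 99/97/92% |
| 36% vs 21% | 25% | 51/47/46% |
| 36% vs 21% | 50% | 0.3/1/2% |

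The all-cause test would pass 36% vs 21% with probability 2.7%. If the CEC attributes exactly the 15-point excess, f = 15/(36 − m) = 43/45/48% and the pass probability is 2.1/2.4/2.7%, which is nominal.

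**The case against.** **The definition is not hidden.** The SAP states it in three sections, and SAP 3.2 points to 10.3.4.1.1 as revised. That stands against any suggestion of concealment. The entry still does not name the requirement that changes which events count.

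**The large swings in step 5 come from assumed over- or under-attribution.** This also stands. The high pass rates at 36% vs 21% need the CEC to miss about half or more of a real excess; the failures at 19% vs 21% need heavy attribution in an arm with no net excess. Protocol 2.3.5.1 reserves *not related* for events clearly due to other causes, which works against under-attribution. Those definitions are addressed to the investigator; the CEC's own criteria are not shown. The rows show dependence on attribution and predict nothing.

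**IMRT-related toxicity is not lost.** Partly right. Grade 2 or higher rectal events lasting at least 5 days are compared between arms, and both SAP 10.2 and SAP 10.3.5.1 admit IMRT-related ones. Adverse event tables and the EPIC bowel domain add to this. But Grade 1 events decide the co-primary, and SAP 10.3.4.1.3 has no non-inferiority test on the protocol definition.

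**The union reading is not certain.** The title of SAP Table 14.2.2.1 mentions rectal events only. On the intersection reading, the main SAP addition is the device-related route. The definitions still differ.

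**Stronger inferences a reader might draw.** One is that the SAP definition favours the balloon. The documents do not support that: few attributions could hide an excess, while many could fail a device with no net harm. Another is that 21% is too high for a marking-only Control rate. No figure in the documents shows this. Nor can a missing source for the rates or margin be pressed, since some pages are not in the available text.

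**Conclusion.** The two documents define different co-primary safety endpoints, and the difference is not itemised. This rests on the wording alone and holds on either reading of the protocol's *and*. The list of dropped events (IMRT-only rectal, non-rectal procedure-related) rests on the union reading, which the protocol's own parallel text favours.

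The 85% is unsupported for the SAP endpoint; it is not miscalculated. Depending on the rates that apply, true power could be higher or lower. The fall in the pass limit from 32 to 12–16 balloon events rests on my assumption of 0 to 3 Control events.

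The SAP test is not invalid: its type I error is near nominal. The problem is what is compared, and that one arm's result depends on attribution routes the other arm does not have.

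**What to change.** Before database lock:

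1. Reconcile Protocol 2.2.2.3 and 2.3.4.1 with SAP 3.1, 5 and 10.3.4.1.1 so that one definition is primary. Itemise any departure from the protocol in SAP 3.2, with its reason.
2. If the SAP definition stays primary, add to SAP 10.3.4.1.3 the same Farrington-Manning test on the protocol definition: a rectal event of Grade 1 or higher from any cause, or an implantation-procedure-related event, each lasting at least 2 days. If the protocol definition is primary, report the attributed version as supportive.
3. In SAP 6, state which endpoint the 21% and 19% describe. Then restate per-arm rates and power for the endpoint tested, or say that the 85% applies to the protocol endpoint only.
4. Separately, reconcile the Grade 2 endpoint. SAP 10.2 requires a rectal event that is also device-, procedure- or IMRT-related. SAP 10.3.5.1 joins its conditions with *or*, so any device- or procedure-related event would count whatever its grade or duration. Correct the title of Table 14.2.3 ("Grade 2 or Greater Rectal or Procedure-Related Events of Duration of Two or More" Days), which conflicts with the 5-day minimum.

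The cost is SAP wording and one extra analysis. The CEC already classifies rectal, device, procedure and IMRT relatedness (SAP 10.3.6.1). The duration of non-rectal procedure-related events must be derivable from adverse event dates. The restated power may be less favourable: at 136 and 68, exact power is 75% if both arms are at 21%, and 61% at 23% balloon against 21% Control.

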2.2.6.5 BALLOON AND MARKER IMPLANTATION, EVALUATIONS AND DATA COLLECTION

Prior to the implantation procedure subjects in *BOTH Groups* will receive an enema per center standard for marking the prostate and may receive medication to relieve anxiety. This should be recorded in the medications eData file.

For the *Balloon Group*, urethral catheterization is recommended at the beginning of the implantation procedure to drain the bladder and aid the positioning of the balloon. At the end of the procedure (or per local standards) the catheter should be removed.

The term "Investigator" refers to the radiation oncologist who is in charge of the planning and the IMRT treatments. However, the implantation procedure may be done by the radiation oncologist, or by a urologist who is proficient in performing transperineal procedures via transrectal Ultrasound guidance. Additionally, Investigator performing the simulation may be done by an oncologist, a medical physist, or other qualified person

This protocol requires prostate marking for *all subjects* in both study arms (*Control and Balloon Groups*). Therefore, this visit must be carried out at the location where the marking is usually done by the respective center (OR, Brachytherapy suit, etc.) by the same physician that will be inserting the balloon.

For *both groups*, the marking *MUST* be done transperineally (not transrectally). This technique will avoid potential puncture of the balloon by a marker in the *Balloon Group* and minimize the potential for data bias due to different insertion techniques.

Note: the enema must employ the same protocol for prepping the rectum as would be employed if the marking was being performed transrectally.

The insertion of the balloon will be done using a free-hand approach with the aid of a trans rectal US. Any form of anesthesia may be utilized at the discretion of the implanting physician. However, whenever possible, each center should remain consistent with the choice of anesthesia to avoid potential differences in temporary post-operative sequelae. The subject may receive local, spinal or general anesthesia. However, the subject should be at least relaxed medically to prevent accidental movement.

For Balloon Group subjects, the balloon implantation will be performed after the marking, and will be performed by a urologist/physician who will be trained by the company for balloon insertion.

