#### 10.3.5.1 Secondary Safety Endpoints

#### Secondary Safety Endpoint #1: Grade 2 Adverse Events

As with the primary safety endpoint, the adverse events qualifying for this secondary safety endpoint will be determined through adjudication by the CEC. This secondary safety endpoint is based on the occurrence of one or more adverse event as follows, as indicated on the CEC CRF:

- Event is indicated to be a Grade 2 or greater Rectal event lasting at least 5 days through the first 183 days (6 months) or
- Event meets one of the relatedness classifications:
  - Event is indicated to possible, probably, or definitely device-related;
  - Event is related to marking or
  - Event is related to the balloon implantation procedure.

As with the primary safety endpoint, subjects will be counted as having an event if one occurs anytime through Day 183 (6 months) from the marking date or as not having an event if they record no events and are followed through at least Day 169 (6 month minus 14 days) from the marking date. This analysis will be based on the CEC classification as identified in Section 10.3.4.1.1. To compare the event rate of the *ProSpace Group* with that of the *Control Group*, the adverse event endpoint will be analyzed using a Fisher's exact test.

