#### 10.3.6 Safety

#### 10.3.6.1 Adverse Events

An adverse event (AE) is as any clinically significant unfavorable and unintended medical occurrence, including any abnormal sign (e.g., physical exam), symptom, or disease, whether or not it is considered related to the device being studied in a subject.

Adverse event severity will be graded from 1-5, according to the Common Terminology Criteria for Adverse Events (CTCAE) (Version 4.0) as provided by the US Department of Health and Human Services, NIH, and the National Cancer Institute.

Adverse Events will be categorized with respect to relationship to the device as "not related", "possibly related", "probably related", or "definitely related", as well as by degree of severity.

Statistical Analysis Dlan	Client/Project	BioProtect BP-007
Statistical Analysis Flan	Version and Date	V2 05-DEC-2021

AEs will be characterized by CEC adjudication, when available, for marking/implantation procedurerelatedness, device-relatedness, IMRT-relatedness, rectum-relatedness, and seriousness. Marking/implantation procedure relatedness adjudication will be further subdivided into relatedness to ProSpace implantation, marker implantation, administration of anesthesia, and use of foley catheter. If there are AEs for which the CEC determination for procedure relatedness or seriousness differs from the determination of the study site, the site-reported AE determinations will be listed separately.

Any AEs reported prior to the marking/implantation procedure will be listed as medical history. AEs that begin during or after the marking/implantation procedure will be counted and listed as AEs. If an AE is specified as starting before the marking/implantation procedure, any event with an increase in severity reported during or after the procedure will be counted and listed as an AE. All AEs will be summarized by treatment group.

Unless otherwise specified, summary counts of AEs will be the number of subjects reporting AEs and not the number of events reported. If the same AE is reported multiple times for the same subject, it will only appear once for that specified treatment and category in the summary tables.

The following AE summaries will be provided:

- Overall Summary of AEs, which will summarize all events, all device-related events, all procedure-related events, all serious events, all device-related serious events, and all procedure-related serious events
- All AEs by Type

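### The SAP classes Foley-catheter events as not implantation-related, although the protocol recommends the catheter for the balloon arm as part of implantation; this can favour the balloon in the Grade 2 endpoint as SAP 10.3.5.1 defines it

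*SAP*

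**What the plan says.** **The catheter in the protocol.** Section 2.2.6.5 says of subjects in the balloon arm: "urethral catheterization is recommended at the beginning of the implantation procedure to drain the bladder and aid the positioning of the balloon". No matching recommendation is made for Control.

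**The protocol's endpoints.** Section 2.3.4.1 bases the primary safety endpoint on "the occurrence of Grade 1 or greater rectal adverse events and implantation procedure related adverse events with a duration of at least 2 days". The secondary endpoint in 2.3.4.5 is "The rate of Grade 2 or greater rectal or implantation procedure related adverse events with a duration of at least 5 days", and 2.3.3 gives a similar union for the labelling test. None of these excludes catheter events.

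**The SAP's rule.** Section 10.3.4.1.1 adds: "Note that events related to anesthesia or to the use of a foley catheter will not be considered marking or implantation procedure-related". Section 3.2 lists this as a clarification and gives no reason for it.

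**The SAP's co-primary.** The same section requires two things at once. The first is "Event is indicated to be a Grade 1 or greater rectal event lasting at least 2 days through the first 183 days (6 months) and"; the second is a relatedness class (device, marking or implantation).

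**The SAP's Grade 2 endpoint.** Section 10.3.5.1 joins the rectal condition and the relatedness condition with *or*, and adds: "This analysis will be based on the CEC classification as identified in Section 10.3.4.1.1". Section 10.2, which sets out the labelling tests, describes the same endpoint as rectal events that are *also* related.

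**General adverse event reporting.** Section 10.3.6.1 subdivides marking/implantation procedure relatedness into balloon implantation, marker implantation, "administration of anesthesia, and use of foley catheter".

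**The concern.** By the protocol's own description, the catheter helps to place the balloon. An injury or infection from it would ordinarily count as a consequence of implantation. The SAP says that it is not one, and so narrows what counts as procedure-related in a way that the protocol endpoints do not.

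The exclusion is worded the same for both arms but does not act equally on them, because the recommendation applies to one arm only. The Grade 2 comparison is one of the two-sided superiority tests meant to support a labelling claim once both co-primaries succeed. Removing events mainly from the balloon arm pushes that test towards a claim in its favour.

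The note also has no rule for an event related to both catheter and implantation. Read literally, such an event leaves the procedure-related route as well.

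**Working it through.** **Step 1. Where the note can act.** Take a balloon subject with a Grade 2 catheter-related urinary event lasting 6 days, not judged device-related, and no other qualifying event.

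| Definition | Counts without the note | Counts with the note |
|---|---|---|
| SAP 10.3.4.1.1 co-primary (rectal *and* related) | No, not rectal | No |
| SAP 10.2 Grade 2 test (rectal *and* related) | No, not rectal | No |
| SAP 10.3.5.1 Grade 2 endpoint (rectal *or* related) | Yes | No |
| Protocol 2.3.3 and 2.3.4.5 (union) | Yes | The protocol has no such note |

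The note changes this subject's outcome only under 10.3.5.1. (As printed, the relatedness limb there repeats neither the grade nor the duration; I take both to be intended.)

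**Step 2. Inputs from the plan.** There are 136 balloon and 68 control evaluable subjects (protocol 2.3.4.4, SAP 6). The test is a two-sided Fisher test at 0.05/3 = 0.0167 (SAP 10.2), or about 0.8% per side. As a check on the setting, the plan's 85% power for the safety co-primary (19% v 21%, margin 15%, one-sided 0.025, Farrington-Manning) reproduces: 85.1% asymptotically and 86.0% by exact enumeration. The plan gives no power or event rate for the Grade 2 test.

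**Step 3. Assumed inputs.** The true Grade 2 rate, with catheter events counted, is 15% in both arms, so any claim for the balloon is false. A share *d* of balloon subjects qualify only through the catheter and are dropped. No control subject is dropped. The documents give neither the 15% nor *d*.

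**Step 4. Formula.** With b(k; n, p) the binomial probability,

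P(false claim) = Σ b(x; 136, 0.15 − d) · b(y; 68, 0.15),

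summed over all (x, y) with x/136 < y/68 and Fisher p ≤ 0.0167. For example, with 10/68 control events (14.7%), 6/136 balloon events (4.4%) give p = 0.014 and a claim; 7/136 give p = 0.030 and none.

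**Step 5. Results.**

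| Points dropped (d) | Balloon men dropped (136 × d) | Balloon rate analysed | P(false claim) |
|---|---|---|---|
| 0 | 0 | 15% | 0.7% |
| 1 | 1.4 | 14% | 1.2% |
| 2 | 2.7 | 13% | 1.9% |
| 3 | 4.1 | 12% | 3.2% |
| 5 | 6.8 | 10% | 7.9% |

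The 15% base is not critical. With 3 points dropped and a total rate of 10%, 15%, 20% or 25% in both arms, the result is 4.3%, 3.2%, 2.7% or 2.4%. These figures are for the Fisher test itself, which is run only if both co-primaries succeed.

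**The case against.** **The labelling test may not be affected.** SAP 10.2 is where the 0.0167 test is set out, and it requires a rectal event. If it governs, a urinary catheter event is out with or without the note, and the table in Step 5 does not apply. This objection stands. The *or* in 10.3.5.1 does agree with the protocol and with the title of SAP Table 14.2.3, but that title gives a duration of two days where the text gives five, so it settles little. The conflict has to be resolved before the effect of the note is known.

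**The rates may be small.** To be dropped, a subject needs a Grade 2 or worse catheter event of at least 5 days and no other route into the endpoint. The protocol has the catheter removed at the end of the procedure or per local standards. At 1 point the chance of a false claim is 1.2%. This also stands: the direction is firm where catheter use is concentrated in the balloon arm, but the size is not known.

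**Sections 10.3.4.1.1 and 10.3.6.1 may be compatible.** The subdivision in 10.3.6.1 can be read as the tool that lets the CEC apply the exclusion. That is a fair reading, so this is a tension and not a flat contradiction. It still leaves two meanings of procedure-related in one SAP.

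**Stronger readings that the documents do not support.**
- A reader might infer that only balloon subjects can suffer catheter harm. Catheterization is recommended, not required, in that arm, and nothing bars it in Control.
- A reader might infer that the harm disappears from the safety comparison. The separate route "Event is indicated to possible, probably, or definitely device-related" stays open, and all adverse events are summarized by group. Those summaries are descriptive, however, and do not correct the test.
- A reader might infer that the non-inferiority test is distorted. That would need the protocol's broad endpoint combined with an exclusion found only in the SAP, and neither document plans that analysis.

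**Conclusion.** The concern holds in a limited form. The SAP removes from the procedure-related class a type of harm that the protocol makes more likely in the balloon arm, without a stated reason and without a counterpart in the protocol's endpoints. Where catheter use is concentrated in that arm, the exclusion can only favour the balloon.

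Its effect on the SAP's co-primary safety endpoint is negligible, since catheter events are rarely rectal. It matters for the Grade 2 endpoint as SAP 10.3.5.1 defines it, and hardly at all as SAP 10.2 defines it. Under 10.3.5.1, the chance of a false balloon-favouring claim goes from 0.7% to between 1.2% and 7.9% as 1 to 5 points of balloon-arm events are dropped. That range rests on an assumed 15% total rate in both arms, no events dropped in Control, and the evaluable numbers in the plan.

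The primary-safety sensitivity analyses in SAP 10.3.4.1.3 do not restore these events, and none is stated for the Grade 2 endpoint.

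**What to change.** 1. Reconcile SAP 10.2 and 10.3.5.1 so that the Grade 2 endpoint has one definition, *and* or *or*, with grade and duration attached to each limb to which they apply. Bring the title of Table 14.2.3 into line.
2. Remove the Foley clause from the note in SAP 10.3.4.1.1 and from SAP 3.2. State that, for the Grade 2 endpoint and any procedure-related component, Foley-related events count as implantation procedure-related in both arms, including events with mixed catheter and implantation cause.
3. Report the version that excludes them as a sensitivity analysis.

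At minimum, keep the note and add a catheter-inclusive sensitivity analysis for the Grade 2 endpoint.

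The cost is SAP wording and one extra table. No new data are needed, because the CEC already adjudicates Foley relatedness separately (SAP 10.3.6.1). The downside for the sponsor is that the balloon arm's event rate may be slightly higher.
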